6.1.2 ANALYSIS OF THE SECONDARY ENDPOINT(S)

The secondary analyses are not dependent on the findings of the primary endpoint. No adjustment for Type 1 errors will be used as only one or a few statistical tests will be conducted for each secondary endpoint.

The secondary endpoints are time to healing and measures listed in Table 1. Each secondary endpoint is measured between one and five occasions during the study. The ITT dataset will be used for all analyses of secondary endpoints. Adjusted analyses will only be conducted for certain secondary endpoints that are of particular interest.

Time to healing will be compared between the study groups using survival analysis. Kaplan-Meier survival curves will be produced for the two study groups with median healing times and 95 % CI. Participants for whom the ulcer has not healed will be treated as censored and their date of trial exit or date of last available assessment will be used to calculate their duration in the trial. Hazard ratio with

95% CIs will be presented. Treatment effect will be explored using a Cox proportional hazards model including stratification factors (ulcer area and depth at baseline, periphery artery disease and infection grade) initially.

Survival analysis as above (but without adjustment) will also be used to compare ulcer recurrence after healing between the study groups. Recurrence rates at 12 months after healing will also be compared.

The analysis of the other secondary endpoints will be conducted according to scale level (nominal, ordinal or interval; Table 1) and compared at each time point (base-line, 4 weeks into treatment and 1, 6 and 12 months post-treatment) using the ITT dataset without adjustment for covariates: t-tests for ordinal and interval data if the assumptions of the t-test is fulfilled (normal distribution and equal variances), otherwise Wilcoxon rank sum test will be used. The Chi-squared test or generalized linear regression method will be used for nominal scale data. For each comparison both exact p-values and two-sided 95% CI will be reported.

The health economic analysis will be a cost-utility analysis that compare the interventions (sealed shoe and cast): treatment costs, quality of life during and after treatment, sick leave from work, and health care consumption. Effects on quality of life will be assess with EQ-5D-5L and SF-36 that makes it possible to express effects on quality of life in terms of quality-adjusted life years. The perspective of the analysis will be societal and take effects from the treatment start to 12 month after treatment end into account. Questionnaires, patient administrative systems, and the Swedish Social Insurance Agency's system will be used as data sources.

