1.2 HYPOTHESES AND OBJECTIVES

The overarching objective is to evaluate whether sealed shoe can heal DFU at least as effectively as TCC, but with fewer adverse events during the treatment period, better long-term effects and to a lower cost.

Specific objectives

Objective 1. To investigate whether a sealed shoe can heal DFUs at least as effectively as TCC (non-inferiority, one-sided hypothesis testing).

Objective 2. To investigate whether there is a difference in adverse events during the treatment period with sealed shoe and TCC (superiority, two-sided hypothesis testing).

Objective 3. To investigate whether there is a difference in long-term effects (up to 12 months after end of treatment) with sealed shoe and TCC (superiority, two-sided hypothesis testing).

Objective 4. To investigate whether there is a difference in health economic outcomes between treatment with sealed shoe and TCC (superiority, two-sided hypothesis testing).

The null hypotheses are that a sealed therapeutic shoe does not heal DFUs at effectively as TCC, and that there are no differences between sealed shoe and TCC in side-effects, long-term effects and health economic outcomes.

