3 STATISTICAL PRINCIPLES

3.1 CONFIDENCE INTERVALS AND P VALUES

In all analyses a 95% confidence level will be used as a cut off to declare statistical significance, and report both exact p-values and 95% CI. One-sided tests and CI will be used for the primary outcome and two-sided tests and CI the secondary outcomes. No adjustment for multiple comparisons will be used.

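### The per-endpoint reason for not controlling Type 1 error does not cover objectives 2–4, each a superiority hypothesis with many post-baseline tests and no deciding endpoint or visit

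*SAP*

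**What the plan says.** SAP 3.1 sets one threshold for everything: "In all analyses a 95% confidence level will be used as a cut off to declare statistical significance". It adds "One-sided tests and CI will be used for the primary outcome and two-sided tests and CI the secondary outcomes" and then "No adjustment for multiple comparisons will be used".

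SAP 6.1.2 gives the reason: "No adjustment for Type 1 errors will be used as only one or a few statistical tests will be conducted for each secondary endpoint". The same section defines the family ("The secondary endpoints are time to healing and measures listed in Table 1") and its repetition ("Each secondary endpoint is measured between one and five occasions during the study"). Apart from time to healing and ulcer recurrence, which get survival analyses, the measures are to be "compared at each time point (base-line, 4 weeks into treatment and 1, 6 and 12 months post-treatment", with an exact p-value and a two-sided 95% CI for each comparison. The section also makes the secondary analyses independent of the primary result.

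SAP 1.2 labels objectives 2, 3 and 4 as superiority objectives with two-sided hypothesis tests. The corresponding null is that "there are no differences between sealed shoe and TCC in side-effects, long-term effects and health economic outcomes". SAP 2.4 places all secondary outcomes in the superiority framework. Neither document names a key secondary endpoint, a deciding visit, a hierarchy, or a rule for when objective 2, 3 or 4 is met.

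**The concern.** The reason given looks at the wrong family. A small number of tests per endpoint limits the error for that endpoint. It says nothing about an objective that about 15 endpoints serve at several visits each. If the conclusion is drawn per objective, the error rate has to be considered per objective.

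This matters because the overarching objective in SAP 1.2 is healing at least as good as with the cast, combined with fewer adverse events, better long-term effects and lower cost. The last three parts rest entirely on secondary comparisons. With significance declared at 0.05 on every row and visit, and nothing to say which result decides, an isolated nominal finding could be presented as support for an objective whatever the primary result.

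A smaller, separate matter is that the list of tested time points includes baseline. In a randomised trial a between-group difference there is due to chance, so the test answers no useful question.

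**Working it through.** The plan states neither a total number of secondary tests nor a family-wise error rate, so there is no figure of its own to reproduce.

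**Step 1: count the tests.** Marks in SAP Table 1, leaving out ulcer healing (the primary outcome):

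- skin complications: 3
- ten rows with 5 marks (HbA1c, BMI, 10-metre walk, timed up and go, Berg, calf circumference, general quality of life, DFS-SF, ActivPAL, activity questions): 50
- five rows with 4 marks (bone density, locus of control, ankle range of motion, ankle strength, shoe adherence): 20
- treatment satisfaction: 2
- new ulcers, amputations, death and Charcot foot: 2
- health care consumption: 3
- sick leave: 3

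The total is 3 + 50 + 20 + 2 + 2 + 3 + 3 = 83 over 20 rows. Sixteen are at baseline, which leaves 67 after baseline. By visit these are 12 (4 weeks) + 19 (1 month) + 18 (6 months) + 18 (12 months). Without ActivPAL, which SAP 6.1.7 treats as mainly exploratory, 67 − 4 = 63.

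**Step 2: allocate tests to objectives.** The Specific aim column in the protocol's Table 1 links rows to aims. Many rows serve more than one aim, so the counts overlap.

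- Objective 2 (during treatment): 12 at 4 weeks. All post-baseline marks on aim-2 rows: 12 + 16 + 14 + 14 = 56. SAP 6.1.3 adds four Chi-square comparisons (AE, SAE, ADE, SADE).
- Objective 3 (1, 6 and 12 months after treatment): 14 + 15 + 15 = 44.
- Objective 4: 1 + 3 + 3 + 3 = 10.

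**Step 3: chance of at least one p < 0.05 with no true effect.** For *k* independent tests this is 1 − 0.95^k; for example, 1 − 0.95^44 = 0.895. With a common pairwise correlation ρ, condition on a shared standard normal *g*: the chance is 1 − ∫ φ(g)·[Φ((1.96 − √ρ·g)/√(1−ρ)) − Φ((−1.96 − √ρ·g)/√(1−ρ))]^k dg. The documents give no correlations, so the range of ρ is an assumption.

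| Family | k | Expected false positives (0.05k) | ρ = 0 | ρ = 0.5 | ρ = 0.7 |
|---|---|---|---|---|---|
| Objective 2, safety categories only | 4 | 0.2 | 19% | 16% | 13% |
| Objective 2, four-week rows | 12 | 0.6 | 46% | 32% | 23% |
| Objective 2, all post-baseline aim-2 rows | 56 | 2.8 | 94% | 65% | 42% |
| Objective 3 | 44 | 2.2 | 90% | 59% | 39% |
| Objective 4 | 10 | 0.5 | 40% | 29% | 21% |
| All post-baseline, pooled | 67 | 3.35 | 97% | 69% | 44% |

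**Step 4: a second correlation structure.** A simulation with higher correlation within a row (0.5–0.8) than between rows (0.1–0.5) gives 55–84% for objective 3, 32–45% for the 12 four-week tests, 59–90% for all 56 aim-2 tests and 24–35% for objective 4. All lie inside the ranges above.

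**Step 5: what is left out.** The counts omit time to healing, recurrence (survival analysis and 12-month rate) and the subgroups in SAP 6.1.5. RAND-36 and EQ-5D-5L share one row, as do new ulcers, amputations, death and Charcot foot; testing them separately would raise the counts. In the other direction, tests on rare events tend to have a true size below 5%, and health care consumption and sick leave are footnoted as inputs to the health-economic analysis.

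**The case against.** The SAP is open about not adjusting and asks for exact p-values and confidence intervals, so a reader can discount the results. That stands as a defence of transparency. It does not make the stated reason valid, and SAP 3.1 still declares significance at the same cut-off in all analyses.

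Several stronger readings are tempting, and the documents do not support them:

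- *That 83 tests contradict the SAP's premise.* They do not. Each row has 2 to 5 marks, which fits a small number per endpoint. The premise is accurate but concerns the wrong family.
- *That baseline tests help an objective to be met by chance.* A baseline difference cannot show fewer adverse events, better long-term effects or lower cost. The relevant count is 67.
- *That a significant secondary result is almost guaranteed.* This holds only near independence. Repeated visits on one row, and overlapping gait, balance and quality-of-life measures, are likely to be correlated. The pooled range is 44–97%, and the pooled figure is not per objective.
- *That one significant row is enough to meet an objective.* No such rule is written. The defect is that no rule is written at all.
- *That objective 4 is exposed like the others.* SAP 6.1.2 plans a cost-utility analysis for it. Its main gap is that SAP 1.2 calls it hypothesis testing while the planned analysis states no test or decision rule.
- *That the secondary tests must wait for non-inferiority.* SAP 6.1.2 deliberately makes them independent of the primary result, and adverse-event comparisons remain informative whatever the healing result. A gate is a choice, not a necessity.

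**Conclusion.** The point holds in limited form. The reason given in SAP 6.1.2 does not justify the absence of error control for objectives 2–4, and as written the unadjusted p-values cannot support confirmatory claims on them.

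The problem is largest for objective 3, where the chance of at least one false positive is about 39–90%. For objective 2 it depends on what is taken to decide the objective: the four safety categories alone carry a modest inflation, the Table 1 rows a large one. Objective 4 is the weakest case. Even the lowest figure, 13%, is more than twice the nominal 5%.

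The sizes assume no true effect, tests of exactly 5% size and pairwise correlations between 0 and 0.7. They also take the protocol's Specific aim column as the link between rows and objectives. The primary conclusion is not affected. This should be corrected, but it does not threaten the main result.

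**What to change.** In SAP 3.1 and 6.1.2:

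1. Delete the per-endpoint justification. State that secondary comparisons are reported as estimates with 95% CIs and nominal p-values, without claims of statistical significance.
2. If a formal claim is wanted for an objective, name one endpoint and one visit for it in advance and control the error across the named tests. Three independent tests at 0.05 each give 1 − 0.95³ = 14.3%. At 0.05/3 = 0.0167 each they give 4.9%. A fixed testing order is an alternative. A gate on non-inferiority is optional.
3. Remove baseline from the list of tested time points, and report baseline values descriptively by group, as SAP 6.1.4 already does for the baseline characteristics.

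The cost is SAP wording and fewer formal secondary claims. No data are lost, and every post-baseline estimate is still reported.

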4.2 ELIGIBILITY

All patients attending the multidisciplinary diabetic foot teams at the study centers during the screening period will be assessed for eligibility.

Inclusion criteria: at least 18 years old, diagnosed diabetes mellitus (all types) and foot ulcer under metatarsal heads. A foot ulcer is here defined as “a break of the skin of the foot that includes minimally the epidermis and part of the dermis.”³⁰

Exclusion criteria: large ulcers (covering 3-5 metatarsal heads), toe pressure or TcPO₂ <30 mmHg, infection of IWGDF grade 3 (if uncontrolled or treatment has not been administered) or IWGDF grade 4, life expectancy <1 year, active Charcot foot, need of custom-made shoe, and inability to read or write Swedish. In addition, people will be excluded where dementia, language- or other communication difficulties, active alcohol or substance abuse, or other factors increase the risk that adverse events or adverse device effects will not be noted or reported, if the person does not have adequate social support.

The eligibility data will be summarized as number of patients screened, number of patients who fulfilled the inclusion criteria, and the number of the patients fulfilling the inclusion criteria that were excluded due to violating each exclusion criterion or who declined to participate. In addition, the number of ineligible patients randomized, if any, will be reported, with reasons for ineligibility.

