4.4 WITHDRAW / FOLLOW-UP

There are several timings of possible withdrawal/lost to follow-up: before base-line assessment, before the intervention has been administered, during the intervention period, and before each follow-up assessment. Reasons include, but are not restricted to, clinical reasons, death, refusal to continue treatment or follow-up, unable to make contact with the participant, etc.

Number of participants, reasons and timing of withdrawal/lost to follow-up will be presented by intervention arm in a CONSORT flow diagram (point 4.3)

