5.3 SAFETY ASSESSMENTS

5.3.1 ADVERSE EVENTS

Adverse events that are judged to be related to the offloading devices (shoe or TCC) will be classified as adverse device effects (ADE) and serious adverse device effects (SADE).³² ADE include, but are not limited to, skin abrasions, blisters, sleep disturbances, issues with gait and balance, etc. SADE include, but are not limited to, new foot ulcers that result in amputation (major amputation = above ankle, minor amputation = below ankle), sepsis, etc.

Averse events that are not related to the offloading devices are classified as adverse events (AE) and serious adverse events (SAE).³² AE include, but are not limited to, skin abrasions or new foot ulcers on the contralateral foot and not related to the device, etc. SAE include, but are not limited to, death, amputation, onset of acute Charcot foot, sepsis, etc. (not related to the offloading device). However, in accordance with previous studies on similar patient populations, not all AE and SAE will be included as the patient population suffers from multiple co-morbidities and therefore a high incidence of illness and hospital admissions unrelated to the DFU and offloading devices can be expected.³³ Therefore, all ADE and SADE will be assessed, but only certain types of AE and SAE that are of particular interest, such as, amputation, death and onset of acute Charcot foot.

ADE, SADE, AE and SAE will be assessed with the aid of questionnaires, CRF, photographs of ulcer and skin, and patient files.

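### Time to healing censors deaths and index-site amputations, so the Kaplan-Meier healing curves read somewhat high, and the recurrence comparison is restricted to healers although the SAP calls it ITT

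*SAP*

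**What the plan says.** For time to healing, SAP 6.1.2 gives one rule for everyone who did not heal: "Participants for whom the ulcer has not healed will be treated as censored", with their time in the trial running to exit or to the last assessment. The display is Kaplan-Meier: "Kaplan-Meier survival curves will be produced for the two study groups with median healing times and 95 % CI". A Cox hazard ratio accompanies it.

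SAP 4.4 says of withdrawal and loss to follow-up: "Reasons include, but are not restricted to, clinical reasons, death, refusal to continue treatment or follow-up". Death is therefore one way of leaving the trial. SAP 5.3.1 foresees both terminal events: "SAE include, but are not limited to, death, amputation, onset of acute Charcot foot, sepsis, etc". Amputation is not named in the censoring rule, but an amputated index ulcer has not healed, so the rule's wording takes it in. Neither document plans a cumulative incidence estimate, a competing-risk model or a composite endpoint.

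For recurrence, SAP 6.1.2 says: "Survival analysis as above (but without adjustment) will also be used to compare ulcer recurrence after healing between the study groups". The 12-month recurrence rate is also counted from healing. The same section says: "The ITT dataset will be used for all analyses of secondary endpoints". SAP 3.3 defines that dataset as all randomised participants.

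**The concern.** Kaplan-Meier treats a censored participant as someone who could still have the event later, with the same prospects as those who remain at risk. That cannot be true after death or loss of the index site. The resulting error in each arm's estimated share healed is upward or zero, never downward. The trial asks whether the shoe heals as well as the cast within a 10-point limit (SAP 2.3). Readers will set the healing curves beside the 12-week proportions, and the two need not agree.

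On recurrence, randomisation protects a comparison of everyone allocated. It does not protect a comparison of those who healed, because healing may depend on the device. Fewer reulcerations with the shoe is a benefit the investigators hope to show (Protocol, Aim 3), so the standing of this comparison matters.

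**Working it through.** **Inputs.** The documents give no figure for either survival analysis, so there is no planned value to reproduce. The only healing figure is the 90% at 12 weeks assumed for both arms in SAP 2.3. The share who die or lose the index site before healing is not given. I assume 1%, 2% and 5% by week 12.

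**Healing curve.** Take constant weekly hazards, λ for healing and m for the competing event.

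- When competing events are censored, 1−KM at week 12 is 1 − exp(−12λ). Setting this to 0.90 gives λ = ln(10)/12 = 0.1919.
- The share with a competing event first is c = m/(λ+m) × [1 − exp(−12(λ+m))]. Solve for m at each assumed c.
- True cumulative healing is F = λ/(λ+m) × [1 − exp(−12(λ+m))].
- The KM median is ln(2)/λ = 3.61 weeks. The true median is the time at which cumulative healing reaches 50%.

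| c (assumed) | m per week | 1−KM | F | Excess (points) | True median (weeks) | Shift (days) |
|---|---|---|---|---|---|---|
| 1% | 0.0022 | 90% | 89.3% | 0.7 | 3.63 | 0.1 |
| 2% | 0.0043 | 90% | 88.5% | 1.5 | 3.65 | 0.3 |
| 5% | 0.0111 | 90% | 86.2% | 3.8 | 3.71 | 0.7 |

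For the 2% row: λ+m = 0.1962, 1 − exp(−12 × 0.1962) = 0.905, and F = 0.978 × 0.905 = 0.885.

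**The same check in reverse.** Fix true healing at h = 90%. Then 1−KM = 1 − (1−h−c)^(h/(h+c)), which gives 90.8%, 91.5% and 94.1% for c = 1%, 2% and 5%.

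**Between arms.** With equal c both curves shift equally. If both arms truly heal 90% but c is 5% in one and 2% in the other, 1−KM reads 94.1% against 91.5%, a gap of 2.6 points. The cause-specific hazard ratio is then about 1.15 in favour of the arm with more deaths or amputations.

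**Recurrence.** With 56 per group (SAP 2.3) and 90% healing, about 0.90 × 56 = 50 per arm enter, and about 10% of those randomised do not. To see what selection can do, suppose one arm heals 90% and the other 80%, with no device effect on recurrence. Those who would heal in either arm recur at 30%, and the extra healers at 60% (all assumed).

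- Recurrence among healers: (0.80 × 0.30 + 0.10 × 0.60)/0.90 = 33.3% against 30%. The better-healing arm looks 3.3 points worse.
- Healed and ulcer-free among all randomised: 0.90 × (1 − 0.333) = 60% against 0.80 × 0.70 = 56%. The better-healing arm is ahead.
- With the extra healers recurring at 40% to 80%, the first gap runs from 1.1 to 5.6 points, and the second comparison from 62% to 58% against 56%.

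**The case against.** The strongest reply is that little rides on the curves. The planned between-arm measure for time to healing is a Cox hazard ratio, and censoring competing events is how a cause-specific hazard ratio is fitted. That stands: the ratio is valid and needs only a label. Deaths should also be few, since SAP 4.2 excludes people with "life expectancy <1 year, active Charcot foot, need of custom-made shoe", as well as severe ischaemia and the worst infections. That limits the size, though these exclusions do not rule out amputations.

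A reader might infer several stronger things that the documents do not support:

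- **Every trial exit is a competing event.** An ulcer can heal after its owner leaves the trial. Other exits are ordinary censoring. It may be informative, but its direction cannot be read from the documents.
- **The primary analysis contradicts this one.** SAP 6.1.1 counts a missing 12-week result as not healed. A binary endpoint and a time-to-event endpoint may use different conventions, so this is a reason for a sensitivity analysis and not an error in itself.
- **Healing times are materially shortened.** The shift is under a day at the assumed rates, while ulcers are inspected once or twice a week (SAP 5.2.1).
- **One device is favoured.** That needs unequal event rates, and none are given.
- **The recurrence result will reverse.** The example needs unequal healing, whereas SAP 2.3 plans on 90% in both arms, where this route to bias largely closes.

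It is also fair to say that recurrence requires prior healing, so a healers-only curve is legitimate. SAP Table 1 separately lists new ulcers, amputations and death at 6 and 12 months. That fills the gap only in part, because those visits are timed from treatment end and nothing is said about participants who never healed.

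**Conclusion.** The point holds as a correction to two secondary analyses. As written, SAP 6.1.2 censors deaths and index-site amputations and so overstates each arm's cumulative healing, by about 0.7 to 3.8 points if 1% to 5% have such an event by week 12. That range rests on constant hazards and assumed rates. If all such events came late, the excess would approach zero.

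The recurrence finding needs no assumed rates. A comparison of healers cannot be an analysis of all randomised participants, so SAP 6.1.2 and SAP 3.3 do not fit together. Whether that misleads depends on whether healing differs between the arms, and the numerical example shows only what is possible. The primary endpoint and its non-inferiority test are untouched. The change is worth making before analysis but does not threaten the main conclusion.

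**What to change.** In SAP 6.1.2:

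1. **Time to healing.** Report Aalen-Johansen cumulative incidence, with death and index-site amputation as competing events. Keep the Cox hazard ratio and label it cause-specific. Censor other exits, with one sensitivity analysis that keeps them in the risk set as unhealed to week 12, in line with the primary rule.
2. **Recurrence.** Keep the planned curve and 12-month rate, but label them as conditional on healing, not ITT. Add a comparison in all randomised participants of being alive, healed, without index-foot amputation and ulcer-free at a fixed time from randomisation, with never-healers counted as failures. The clock must start at randomisation, because the planned visits run from healing or treatment end and a never-healer has no such date.

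The costs are slightly less favourable healing curves, a little more analysis, and the recording of dates of death, amputation and new ulcers. The documents name patient files as a source for these events but do not say that their dates are captured, so the case report form should ask for them.
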